The per-protocol analysis set will consist of all subjects in the intent-to-treat analysis set terminating the study without any major deviation of the protocol and its procedures. Subjects with major protocol deviations will be excluded from the per-protocol analysis.

The confirmatory analysis of the primary endpoint variable will be performed both for the intent-to-treat analysis set and the per-protocol analysis set. In Study Part 1 and Study Part 3 all subjects treated with at least one dose of study drug will be included in the efficacy analyses. For all efficacy analyses in Study Part 1 and Study Part 3, subjects will be analyzed according to the treatment they actually received.

All analyses as described in detail in the statistical analysis plan (SAP) will be performed after DBL.

Safety Analyses

Safety data, including but not limited to, AEs, SAEs, infections, serious infections, changes in laboratory assessments, and changes in vital signs will be summarized. Treatment-emergent AEs (TEAEs) will be summarized by treatment group and Medical Dictionary for Regulatory Activities (MedDRA) system organ class and preferred terms.

Pharmacokinetic Analyses

Serum guselkumab concentrations at specified visits will be summarized by efficacy response status for each treatment group. Descriptive statistics, including arithmetic mean, SD, median, interquartile range, minimum, and maximum will be calculated at each sampling time. All concentrations below the lowest quantifiable sample concentration of the assay (below the quantifiable limit; BQL) or missing data will be labeled as such in the concentration data listing or statistical analysis system dataset. The BQL concentrations will be treated as zero in the summary statistics.

Biomarker Analyses

Biomarker samples will be used to define serum markers, skin gene expression and cellular profiles, and genetic (DNA) data for correlative analyses to better understand the molecular effects of guselkumab on the pathogenesis of psoriasis including the differences between >2 years and ≤ 2 years disease duration and to understand why people may respond differently to guselkumab. These analyses are considered exploratory and will be summarized in a separate technical manual.

Statistical Analyses per Study Part

Statistical analyses will be performed for each Study Part.

The confirmatory analysis is planned to be performed at the end of Study Part 2, ie, after all subjects have completed their visit at week 68 (ie, 40 weeks after randomization) or discontinued earlier. This analysis will include the confirmatory analysis of the primary endpoint, and the exploratory analyses of the major secondary endpoints and all other predefined efficacy and safety analyses from week 28 until week 68.

The analyses of Study Part 1 and Study Part 3 will be exploratory. The exploratory analysis of Study Part 1 will occur after all subjects have completed their visit at week 28 (ie, 28 weeks after study inclusion) or discontinued earlier. This analysis will include the safety analysis and all efficacy measures after Week 0 and will cover the time until the week 28 visit. The exploratory analysis of Study Part 3 will occur after all subjects have completed their visits at week 116 (ie, 48 weeks after inclusion in Study Part 3 at week 68) or week 144 in case of subjects entering the re-treatment arm in week 116, at week 164 (ie, 96 weeks after inclusion in Study Part 3 at week 68) or week 192 in case of subjects entering the re-treatment arm in week

164, and at week 220 (ie, 152 weeks after inclusion in Study Part 3 at week 68) or week 248 in case of subjects entering the re-treatment arm in week 220 or discontinued earlier. These analyses will include the safety analyses and all efficacy measurements after week 68 and will cover the time until week 116/164/220 and week 144/192/248, respectively.

TIME AND EVENTS SCHEDULE

Schedule of Study Conduct: Part 1 and 2																			
Study Period	Screening ^b	Part 1 (Therapy Initiation, group 1)					Part 2* for SRe (Blinded Treatment, groups 2a and 2b)					Part 2** for non-SRe (q8w Treatment, group 2c)						ETV ****	
Week	0	4	12	16	20	28	36	44	52	60	68	28	36	44	52	60	68	72 (SFU) *****	
Study Procedures^a																			
Screening/Administrative																			
Informed consent ^c	X																		
Medical history and demographics	X																		
Eligibility criteria	X	X																	
Study Drug Administration																			
Randomization ^d						X													
Stratification							X												
Study drug administration ^e		X	X	X		X	X	X	X	X	X		X	X	X	X	X		
Study drug accountability		X	X	X		X	X	X	X	X	X		X	X	X	X	X		
Safety Assessments																			
Physical examination	X	X				X	X					X	X	X				X	
Vital signs		X-----																X	
Tuberculosis evaluation	X	X	X	X	X	X	X	X	X	X	X	X	X	X	X	X	X		
Chest radiograph ^p	X																		
Urine pregnancy test ^f	X	X	X	X	X	X	X	X	X	X	X	X	X	X	X	X	X		
Height		X																	
Weight		X					X					X	X					X	
Concomitant therapy	X-----																	X	
Adverse events	X-----																	X	

Study Period	Screening ^b	Part 1 (Therapy Initiation, group 1)					Part 2* for SRe (Blinded Treatment, groups 2a and 2b)						Part 2** for non-SRe (q8w Treatment, group 2c)						ETV ****	
		0	4	12	16	20	28	36	44	52	60	68	28	36	44	52	60	68		
Week																				72 (SFU) ****
Efficacy Assessments																				
PASI	X	X	X	X	X	X	X	X	X	X	X	X	X	X	X	X	X	X	X	
NAPPA		X					X			X		X	X			X		X		
BSA		X		X	X		X			X		X	X			X		X		
DLQI ^g	X	X		X	X	X			X		X	X				X		X		
PSSD ^g	X	X		X	X	X			X		X	X				X		X		
TLSS ^h		X	X			X					X	X						X		
Photo documentation ⁱ		X	X	X	X	X	X	X	X	X	X	X	X	X	X	X	X	X	X	
Clinical Laboratory^j																				
QuantiFERON-TB test	X																			
Hepatitis B & C serology	X																			
HIV serology	X																			
Hematology ^k	X	X		X		X		X		X		X		X		X		X	X	
Chemistry ^k	X	X		X		X		X		X		X		X		X		X	X	
Pharmacokinetics																				
Serum guselkumab concentration ^l						X	X	X					X	X						
Biomarkers																				
Serum biomarkers (3) ^l		X	X				X						X	X					X	
Skin biopsy for cellular substudy (1) ^m (optional)		X	X				X						X	X					X	
Skin biopsy for gene expression substudy (2) ^m (optional)		X	X				X						X	X					X	
Whole blood (PBMC) for cellular substudy (1) ⁿ (optional)		X	X				X						X	X					X	
Genetic (DNA) evaluations(4) ^o (optional)		X																		

Schedule of Study Conduct: Part 3														
Study Period	Part 3*** (Withdrawal, groups 3a and 3b)													
	80	92	104	116	128	140	152	164	176	188	200	212	220 (FSV)	ETV ****
Study Procedures^a														
Safety Assessments														
Vital signs	X	X	X	X	X	X	X	X	X	X	X	X	X	
Weight				X			X					X	X	
Concomitant therapy	X	X	X	X	X	X	X	X	X	X	X	X	X	
Adverse events	X	X	X	X	X	X	X	X	X	X	X	X	X	
Efficacy Assessments														
PASI	X	X	X	X	X	X	X	X	X	X	X	X	X	
NAPPA	X		X	X			X					X	X	
BSA	X		X	X		X	X		X		X	X		
DLQI ^g	X	X	X	X		X	X					X	X	
PSSD ^g				X		X	X					X	X	
Photo documentation ⁱ	X	X	X	X	X	X	X	X	X	X	X	X	X	
Biomarkers														
Serum biomarkers (3) ^l	X			X			X					X		
Skin biopsy for cellular substudy (1) ^m (optional)				X								X		
Whole blood (PBMC) for cellular substudy (1) ⁿ (optional)	X			X								X		
Skin biopsy for gene expression substudy (2) ^m (optional)				X								X		
Non-invasive novel method 'tape stripping'				X								X		

BSA = body surface area; DLQI = Dermatology Life Quality Index; ETV = Early Termination Visit; FSV = Final Study Visit; NAPPA = Nail Assessment in Psoriasis and Psoriatic Arthritis (CLIN, PBI and QoL); PASI = Psoriasis Area and Severity Index; PBMC = peripheral blood mononuclear cells; PSSD = Psoriasis Symptom and Sign Diary 7-day version; SFU = Safety-Follow-up visit; TLSS = Target Lesion Severity Scores

Visits through week 68 are to be conducted within ± 7 calendar days and visits after week 68 are to be conducted within ± 14 calendar days; please prospectively contact the Sponsor for further instructions if it is anticipated that a visit may fall outside this window. In the event of early discontinuation of study agent, the assessments should be conducted at the time of discontinuation of study agent (ETV). After ETV, safety follow-up should be conducted for 12 weeks after the last administration of study drug. Subjects who discontinue study agent may or may not continue in the study depending on the reason for discontinuation of study agent; refer to Section 10.2 for further details.

***)**: Only for subjects reaching a PASI score=0 at weeks 20 **and** 28

******): Subjects who will not reach a PASI score=0 at week 20 or week 28 will receive further q8w guselkumab 100 mg treatment until week 60 (last guselkumab administration), with final study assessment at week 68 and final Safety Follow-Up Visit at week 72.

*******): Study Part 3 will last about 152 weeks until week 220 (Final Study Visit) and will not require any administrations of guselkumab. In between the 12-weekly on-site visits, telephone-visits will be done 6 weeks (± 7 days) after each on-site visit (ie, telephone visits at weeks 74, 86, 98, 110, 122, 134, 146, 158, 170, 182, 194, and 206) to notice a possible worsening of psoriasis.

********): For subjects, who withdraw from study participation, every effort should be made to conduct the ETV.

*********): For all subjects (part 1 and part 2) who discontinue study treatment prematurely, every effort should be made to conduct the SFU 12 weeks **after the last study drug administration**.

- a. All study procedures and evaluations are to be completed before study drug injection. Assessments for subjects who discontinue study agent administration or withdraw from the study are described in Section 10.2 and 10.3, respectively.
- b. To occur within 4 weeks prior to week 0.
- c. Informed consent form must be signed before any study-related activity
- d. All subjects reaching a PASI=0 at week 20 **and** 28 will be determined as Super-Responders (SRe) and will be randomized at week 28 in Study Part 2.
- e. Subjects will receive guselkumab 100 mg at the weeks 0, 4, 12 and 20 (Study Part 1), and guselkumab or Placebo q8w at the weeks 28 to 60 (Study Part 2).
- f. Women of childbearing potential must have a negative urine pregnancy test result at all study visits before study treatment drug administration.
- g. Performed by the subject (PRO) before any tests, procedures, or other evaluations (eg, PASI, affected BSA or NAPPA-CLIN) are performed for that visit.
- h. TLSS for the selected target lesion will be recorded at each biopsy collection time.
- i. Photo-documentation will be done standardized and professionally at few selected sites equipped with an appropriate photography laboratory (described in photo-documentation manual).
- j. All blood samples must be collected before study drug administration at visits when a study drug administration is scheduled. Details will be provided in the Laboratory Manual.
- k. Laboratory assessments can be non-fasting and are listed in Section 9.6.
- l. One additional blood sample for pharmacokinetic and serum biomarker assessments will be taken at the time when the subject loses control of disease (defined as PASI score >5 at any visit during Study Parts 2 or 3, or PASI ≥ 3 at week 68).
- m. Biopsy samples for molecular and cellular analyses will be collected only from subjects who consent to participate in the optional biopsy substudy. A total of six 6 mm biopsy samples (or twelve 3 mm biopsy samples in substudy 2, if applicable; refer to Section 3.1) will be collected (1 NL at week 0, 1 L at weeks 0, 4, 28, and 68, and where feasible, 1 biopsy from a relapsing plaque at the time a subject in Study Part 2 or 3 requires re-treatment (see l). For further details regarding these evaluations, refer to Section 9.4. The target lesion will be photo-documented in a standardized manner (described in the Biopsy manual) if the subject agrees to photo-documentation.
- n. Blood samples to isolate PBMC for immunophenotyping analyses will be collected only from subjects who consent to participate in the optional substudy 1. For further details regarding these evaluations, refer to Section 9.4.
- o. Blood samples for genetic (DNA) analyses will be collected only from subjects who sign a separate consent form to participate in the genetic (DNA) evaluations. For further details regarding these evaluations, refer to Section 9.4.
- p. Only if no chest radiograph done within the last 3 months before administration of first study drug.

Schedule of Study Conduct - Part 2 and 3: Re-treatment for subjects with loss of disease control (groups 2d and 3c)*					
Re-treatment Week	R0	R8	R16	R24	R28 (SFU)
Study Procedures^a					
Study Drug Administration					
Study drug administration ^b	X	X	X		
Study drug accountability	X	X	X		
Safety Assessments					
Physical examination	X			X	X
Vital signs	X-----				X-----
Tuberculosis evaluation	X-----				X-----
Urine pregnancy test ^c	X-----				X-----
Weight				X	
Concomitant therapy	X-----				X-----
Adverse events	X-----				X-----
Efficacy Assessments					
PASI	X	X	X	X	
NAPPA	X			X	
BSA				X	
DLQI ^d	X		X	X	
PSSD ^d	X			X	
TLSS ^e	X				
Photo documentation ^f	X	X	X	X	
Clinical Laboratory^g					
Hematology ^h	X		X		X
Chemistry ^h	X		X		X
Pharmacokinetics					
Serum guselkumab concentration ⁱ	X				
Biomarkers					
Serum biomarkers (3) ⁱ	X				
Skin biopsy and blood sample for PBMC for cellular substudy (1) ^{j,k} (optional)	X				
Skin biopsy for gene expression substudy (2) (optional) ^j	X				
Non-invasive novel method 'tape stripping'	X				

BSA = body surface area; DLQI = Dermatology Life Quality Index; NAPPA = Nail Assessment in Psoriasis and Psoriatic Arthritis (CLIN, PBI and QoL); PASI = Psoriasis Area and Severity Index; PSSD = Psoriasis Symptom and Sign Diary 7-day version; SFU = Safety-Follow-up visit; TLSS = Target Lesion Severity Scores

Re-treatment visits are to be conducted within ± 7 calendar days; please prospectively contact the Sponsor for further instructions if it is anticipated that a visit may fall outside this window. In the event of early discontinuation of study agent, these assessments should be conducted at the time of discontinuation of study agent (ETV). After ETV, safety follow-up should be conducted for 12 weeks after the last administration of study drug. Subjects who discontinue study agent may or may not continue in the study depending on the reason for discontinuation of study agent; refer to Section 10.2 for further details.

***)**: Subjects (SRe) with PASI score >5 at any visit in Study Part 2 or 3, or a PASI score ≥ 3 at week 68 will receive guselkumab 100 mg q8w for further 3 administrations (at that visit = re-treatment weeks 0, 8 and 16) and study termination after 28 weeks (Safety-Follow Up visit)

- a. All study procedures and evaluations are to be completed before study drug injection. Assessments for subjects who discontinue study agent administration or withdraw from the study are described in Section 10.2 and 10.3, respectively.
- b. Subjects will receive guselkumab 100 mg q8w for further 3 administrations (re-treatment weeks 0, 8 and 16).
- c. Women of childbearing potential must have a negative urine pregnancy test result at all study visits before study treatment drug administration.
- d. Performed by the subject (PRO) before any tests, procedures, or other evaluations (eg, PASI, affected BSA or NAPPA-CLIN) are performed for that visit.
- e. TLSS for the selected target lesion will be recorded at each biopsy collection time.
- f. Photo-documentation will be done standardized and professionally at few selected sites equipped with an appropriate photography laboratory (described in Photo-documentation manual).
- g. All blood samples must be collected before study drug administration at visits when a study drug administration is scheduled. Details will be provided in the Laboratory Manual.
- h. Laboratory assessments can be non-fasting and are listed in Section 9.6.
- i. One additional blood sample for pharmacokinetic and serum biomarker assessments will be taken at the time when the subject loses control of disease (defined as PASI score >5 at any visit during Study Parts 2 or 3, or PASI ≥ 3 at week 68). However at R0, PK-samples will only be taken for Study Part 2d (ie, not for Study Part 3c).
- j. Biopsy samples for molecular and cellular analyses will be collected only from subjects who consent to participate in the optional biopsy substudy. A total of six 6 mm biopsy samples (or twelve 3 mm biopsy samples in sub 2 if appl., refer to Section 3.1) will be collected (1 NL at week 0, 1 L at weeks 0, 4, 28, and 68, and where feasible, 1 biopsy from a relapsing plaque at the time a subject in Study Part 2 or 3 requires re-treatment (see l). For further details regarding these evaluations, refer to Section 9.4. The target lesion will be photo-documented in a standardized manner (described in the Biopsy manual), if the subject agrees to photo-documentation.
- k. Blood samples to isolate PBMC for immunophenotyping analyses will be collected only from subjects who consent to participate in the optional substudy 1. For further details regarding these evaluations, refer to Section 9.4.

ABBREVIATIONS

AE	adverse event
ALT	alanine aminotransferase
APC	antigen presenting cell
AST	aspartate aminotransferase
BSA	body surface area
CLIN	Clinical
CRF	case report form(s)
DBL	database lock
DLQI	Dermatology Life Quality Index
DMC	Data Monitoring Committee
DNA	deoxyribonucleic acid
eDC	electronic data capture
eg	example given
FSV	Final study visit
GCP	Good Clinical Practice
HBV/HCV	Hepatitis B virus/ Hepatitis C Virus
HIV	human immunodeficiency virus
IB	Investigators Brochure
ICF	informed consent form
ICH	International Council for Harmonisation
ie	that is
IEC	Independent Ethics Committee
IGRA	interferon-gamma-release-assay
IL	Interleukin
IL-23-R	interleukin-23 receptor
IRB	Institutional Review Board
ISR	injection site reaction
IWRS	interactive web response system
mAb	monoclonal antibody
MedDRA	Medical Dictionary for Regulatory Activities
MTX	Methotrexate
NAPPA	Nail Assessment in Psoriasis and Psoriatic Arthritis
NCI-CTCAE	National Cancer Institute Common Terminology Criteria for Adverse Events
PASI	Psoriasis Area and Severity Index
PBI	Patient Benefit Index
PFS-U	Prefilled Syringe assembled with the UltraSafe PLUS™ Passive Needle Guard
PQC	Product Quality Complaint
PRO	patient-reported outcome(s)
PSSD	Psoriasis Symptom and Sign Diary
QoL	quality of life
q8w/q16w	every 8/16 weeks
RNA	ribonucleic acid
SAE	Serious Adverse Event
SAP	Statistical Analysis Plan
SC	Subcutaneous
SRe	Super-Responder(s)
SUSAR	suspected unexpected serious adverse reaction
TB	Tuberculosis
Tc17 cell	IL-17 producing cytotoxic T cell
TES	Time and Events Schedule
Th17 cell	IL-17 producing T helper cell
TLSS	Total Lesion Severity Score
ULN	upper limit normal

DEFINITIONS OF TERMS

PASI < 3: controlled disease
 PASI 3 to 5: fluctuating disease
 PASI >5: loss of control/re-treatment

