Descriptive statistics will include counts and proportions for categorical data, and mean, standard deviation, median, interquartile range, and range for continuous data. Graphical data displays may also be used to summarize the data. The two-group large-sample normal approximation Wald Z-test with Mantel-Haenszel stratum weights for 'disease duration' will be used to compare the proportion of subjects responding to treatment. Continuous response parameters will be compared using an analysis of variance model with fixed effects for treatment group and disease duration and baseline (week 0) value as a covariate. Time-to-event endpoints will be analyzed using Kaplan-Meier product limit methods to estimate the survival distributions and the median time-to-event. The confirmatory significance level for non-inferiority testing is fixed to a one-sided $\alpha=0.05$. Besides the confirmatory testing of the primary endpoint all other inferential statistical testing (including calculation of confidence intervals) is to be interpreted in the exploratory sense only.

Sample Size Determination

The present trial is designed to demonstrate that guselkumab 100 mg q16w treatment is non-inferior to guselkumab 100 mg q8w treatment in SRe as assessed by the proportion of subjects with an absolute PASI score <3 at week 68. A non-inferiority margin of 10% was chosen based on a minimally clinically meaningful difference. Based on data from CNTO1959PSO3002 (IB, Section 4.3.1.5) the proportion of subjects with an absolute PASI score <3 at week 68 is assumed to be 90% for guselkumab 100 mg q8w. The expected difference in proportions between the treatment groups is 0%.

The sample size estimation using the power approach is performed for the per-protocol analysis set as described below. No formal adjustment of the significance level is necessary.

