- Proportion of subjects who achieve a PASI 75/90/100 response at weeks 20, 28, 68, 116, 164, and 220 per study group (**1, 2a, 2b, 2c, 3a, and 3b**)
- Time to loss of disease control (absolute PASI score > 5 at any visit) after treatment withdrawal beyond week 68 per study group (**3a and 3b**)
- Proportion of subjects with an absolute PASI score=0 at all of the following visits: weeks 12, 16, 20, and 28 (**study group 1**)
- Change from baseline (week 0) in Dermatology Life Quality Index (DLQI) score at weeks 28, 68, 116, 164, and 220 per study group (**1, 2a, 2b, 2c, 3a, 3b, and 3c**)
- Proportion of subjects who achieve a DLQI score 0/1 and < 5 at weeks 28, 68, 116, 164, and 220 per study group (**1, 2a, 2b, 2c, 3a, 3b, and 3c**)
- Change from baseline (week 0) in affected Body Surface Area (BSA) at weeks 12, 28, 52, 68, 80, 104, 116, 140, 164, 188, 212, and 220 (**all study groups**)
- Change from baseline (week 0) in the Nail Assessment in Psoriasis and Psoriatic Arthritis (NAPPA) score at weeks 28, 68, 116, 164, and 220 among subjects with nail psoriasis at baseline (week 0; **1, 2a, 2b, 2c, 3a, and 3b**)
- Change from baseline (week 0) in the signs and symptoms aggregate scores of the Psoriasis Symptoms and Signs Diary (PSSD) at weeks 28, 68, 116, 164, and 220 (**1, 2a, 2b, 2c, 3a and 3b**)
- Proportion of subjects who achieve a PSSD sign score=0 at week 68 among subjects with a PSSD sign score ≥ 1 at week 28 per study group (**2a, 2b, and 2c**)
- Association between trough serum guselkumab concentration and efficacy or serum biomarker level
- Association between trough serum guselkumab levels at weeks 20, 28, 36, and 68 and achieving a PASI score < 3 at week 68 per study group (**2a and 2b**)
- Proportion of subjects who were re-treated due to loss of disease control (PASI > 5) and regain control of disease (PASI < 3) 24 weeks after start of re-treatment (study groups **2d and 3c**)
- Safety and tolerability with regard to adverse events (AEs) and abnormal laboratory results (**all study groups**).

Refer to Section 9 for evaluations related to these endpoints.

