3.2. Study Design Rationale

Dose rationale

A dose regimen of guselkumab 100 mg at weeks 0, 4 and q8w thereafter was selected for Study Part 1. This is the dose regimen, which is known to result in clinically meaningful improvement of the disease (SmPC TREMFYA®). In Study Part 2, subjects with a PASI score=0 at weeks 20 and 28 will be randomly assigned to either guselkumab 100 mg q8w or q16w to evaluate if these subjects maintain their disease control (absolute PASI score <3 at week 68) under extended dosing intervals. A larger dosing interval would provide higher comfort and better economy for subjects and physicians.

Duration of treatment period and whole study period

This study will have a 4-week screening phase, a 60-week treatment phase and a 12- to 160-week safety follow-up phase (depending on whether subjects are participating in Study Part 3). The duration of the regular subject's participation allows for an adequate treatment period and provides sufficient time to perform follow-up on safety and maintenance of response.

Blinding and randomization

Randomization will be used to minimize bias in the assignment of subjects to guselkumab 100 mg q8w or q16w (Study Part 2), to increase the likelihood that known and unknown subject attributes (eg, demographic and baseline characteristics) are evenly balanced across treatment groups, and to enhance the validity of statistical comparisons across treatment groups. Double-blinded treatment (Placebo treatment at weeks 28, 44 and 60 for subjects assigned to guselkumab 100 mg q16w) will be used to reduce potential bias during data collection and evaluation of the endpoints. Week 28 was chosen as the time for randomization because it allows subjects to reach steady-state

guselkumab concentrations with a q8w dosing regimen as well as steady-state clinical response. Randomization will be stratified by disease duration at baseline (≤ 2 years vs. >2 years) and by participation in the mechanistical substudy 1 to allow for evaluation of similarities or differences regarding the response rates.

Biomarker and DNA collection

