11.8. Other Analyses

Stratified Newcombe confidence limits for the common proportion difference with respect to the primary endpoint will also be provided by using the method of Yan and Su ([Yan und Su 2010](#)).

In addition, the primary endpoint will also be analyzed without adjustment for disease duration ('unadjusted analysis'). The two-group large-sample normal approximation Z-test ('asymptotic

Wald test of noninferiority') along with the two-sided 90% Wald type and Newcombe confidence interval will be computed.

For binary endpoints in Study Part 2 counts and percentage of subjects per treatment group along with odds ratio (OR), relative risk (RR) and risk difference (RD), two-sided 90% confidence intervals and p-values for treatment comparison based on Mantel-Haenszel weights adjusted for disease duration will be provided.

The change from baseline of continuous endpoints in Study Part 2 will be analyzed by an analysis of covariance model (ANCOVA) with the fixed effect factors for treatment group and disease duration and the baseline value as covariate. The Least-Squares means (LS means), the LS mean difference and the standardized mean difference (computed according to Hedges' g) with the two-sided 90% CI will be provided from the ANCOVA model.

Statistical analyses for time to event endpoints in Study Part 2 will provide the median time-to-even estimates per treatment group with two-sided 90% confidence intervals and the hazard ratio (including two-sided 90% confidence interval) calculated from Cox-regression with the factors treatment group and disease duration as covariate.

Exploration of possible heterogeneity of treatment effects across centers for the primary endpoint will be performed by descriptive frequency statistics including graphical display of the results of the individual centers, as appropriate. No pooling of centers will be performed.

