5.1.4. Baseline and Endpoint

Baseline for Study Part 3 is defined as the last observation (ie, value, measurement) prior to the start of the first study agent administration at baseline (week 0) in Study Part 1.

Endpoint for Study Part 3 is defined as the last available post-baseline result within the analysis period from week 68 until week 116/164/220. Results obtained at unscheduled visits are included in this definition and will be considered as the endpoint value if the unscheduled visit result is the last post-baseline result available within the analysis period from week 68 until week 116/164/220.

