5.5.3.2. Dermatology Life Quality Index (DLQI)

- Change from baseline (week 0) in DLQI score at weeks 116, 164, and 220

The change from baseline in DLQI will be summarized by descriptive statistics using appropriate tabulation. The baseline value, the week 116/164/220 value, and the respective change from baseline value, will be displayed.

A univariate analysis of covariance (ANCOVA) model will be used to test the difference in change from baseline between study groups; the change from baseline being the dependent variable, and former treatment, disease duration, and baseline value of endpoint, as independent variables. A

95% confidence interval for the difference in Least Squares (LS) means and p-value will be calculated based on contrast test statistics. The LS means, the LS mean difference and the standardized mean difference (computed according to Hedges' g), together with the 95% CI and two-sided p-value, will be provided from the ANCOVA model.

- Proportion of subjects who achieve a DLQI score 0/1 and <5 at weeks 116, 164, and 220

The proportion of subjects meeting the response criteria will be displayed in a frequency table providing the number and percentage of subjects per study group (NRI and OC analysis) along with odds ratio (OR), relative risk (RR) and risk difference (RD), and two-sided Wald-type 95% confidence intervals (95% CIs) stratified by 'disease duration'. For single proportions within each study group, unstratified two-sided 95% CIs according to Clopper-Pearson will be calculated. Graphical presentation will be presented by means of bar charts.

The two-group large-sample normal approximation Wald Z-test with Mantel-Haenszel stratum weights for 'disease duration' will be used to compare the proportion of responding subjects among the study groups. The Mantel-Haenszel estimate, the two-sided Wald-type 95% confidence limits, and the test for the difference of proportions will be computed by using Mantel-Haenszel stratum weights (Mantel & Haenszel, 1959) and the Sato variance estimator (Sato 1989).

The respective proportion of subjects will also be given by disease duration category (assessed at baseline, ie, ≤2 years, >2 years) and overall, providing exploratory p-values (unadjusted Chi² test) for the difference between disease duration categories.

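### The 2a-vs-2b ANCOVA of DLQI and PSSD adjusts for the week-0 score but not the week-28 score taken at randomisation, which may cost some precision in exploratory endpoints

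*Protocol*

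**What the plan says.** - **Randomisation.** Protocol 3.2: "Week 28 was chosen as the time for randomization because it allows subjects to reach steady-state" drug concentrations and clinical response. Only subjects with PASI=0 at weeks 20 and 28 are randomised to 2a (q8w) or 2b (q16w).
- **Model.** The Synopsis specifies "fixed effects for treatment group and disease duration and baseline (week 0) value as a covariate". Protocol 11.8 gives the Part 2 model as an "analysis of covariance model (ANCOVA) with the fixed effect factors for treatment group and disease duration and the baseline value as covariate". Sections 11, 11.3 and 11.8 do not repeat the week number, but the endpoint list in 2.1.2 ties baseline to week 0.
- **Endpoints.** Protocol 2.1.2 lists "Change from baseline (week 0) in Dermatology Life Quality Index (DLQI) score at weeks 28, 68, 116, 164, and 220 per study group", and change from week 0 in the aggregate scores of the "Psoriasis Symptoms and Signs Diary (PSSD) at weeks 28, 68, 116, 164, and 220". The week-28 scores are thus scheduled data. Footnotes a and g of the Time and Events Schedule place them before that visit's injection.
- **Part 3.** Part 3 SAP 5.5.3.2 uses "former treatment, disease duration, and baseline value of endpoint, as independent variables" for 3a vs 3b, and 5.5.3.5 does the same for PSSD. Section 5.1.4 fixes the meaning: "Baseline for Study Part 3 is defined as the last observation (ie, value, measurement) prior to the start of the first study agent administration" at week 0.
- **Status.** Both the protocol and the Part 3 SAP class these analyses as exploratory.

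Nowhere do the documents enter the week-28 score in a between-arm model.

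**The concern.** The randomised question is whether control is maintained from week 28 onward. The only score covariate describes the untreated state 28 weeks earlier, when inclusion criterion 3 required DLQI above 10. That restricts its range, and it precedes both effective treatment and selection on clear skin. It is reasonable to expect residual burden at week 28 to predict week 68 better than untreated burden does, though this is an inference.

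A valid pre-randomisation predictor that is already in the database is therefore unused. At stake are the width of the interval for the q16w-minus-q8w difference in patient-reported outcomes and the handling of any chance imbalance at week 28.

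The sponsor follows the phase-start principle elsewhere. Re-treatment SAP 5.1.4 resets baseline to R0, and 5.6.1 and 5.6.6 adjust for it. BSA is not part of the point: with PASI=0 at week 28, affected BSA is essentially zero in every randomised subject.

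**Working it through.** **The plan's own figure.** The only sample size stated is for the primary endpoint. From Protocol 11.2 (90% in both arms, margin 10 points, one-sided 0.05, 80% power): n = 2 × 0.9 × 0.1 × (1.645 + 0.842)² / 0.10² = 111.3, so 112 per arm, and 112/0.8 = 140. Both match and neither is affected. No SD, correlation or power is given for DLQI or PSSD.

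**Formula.** Write r0 for the week-0 to week-68 correlation, r28 for week 28 to week 68, and r for week 0 to week 28. With week 0 in the model, analysing change from week 0 or the week-68 value gives the same treatment estimate. Ignoring degrees of freedom, and with disease duration in both models:

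- R² = (r0² + r28² − 2·r0·r28·r) / (1 − r²)
- variance ratio, both scores against week 0 only = (1 − R²) / (1 − r0²)
- narrowing of the interval = 1 − √(variance ratio)

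**Worked case**, r0 = r = 0.2 and r28 = 0.5, all assumed: R² = (0.04 + 0.25 − 0.04)/0.96 = 0.2604. The ratio is 0.7396/0.96 = 0.770, its square root 0.878, and the narrowing 12.2%.

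**Range**, r0 = r = 0.2 throughout. The last column is 280 × (1 − variance ratio).

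| r28 | Variance ratio | Interval narrower by | Subjects of 280 |
|---|---|---|---|
| 0 | 0.998 | 0.1% | 0 |
| 0.2 | 0.972 | 1.4% | 8 |
| 0.3 | 0.927 | 3.7% | 21 |
| 0.4 | 0.859 | 7.3% | 39 |
| 0.5 | 0.770 | 12.2% | 64 |
| 0.6 | 0.660 | 18.8% | 95 |

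Varying r0 from 0 to 0.3 changes little: 2.1% to 1.1% at r28 = 0.2, and 14.0% to 11.8% at r28 = 0.5.

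**Floor check.** A simulation used 140 per arm, week-0 DLQI above 10, and scores floored at 0 at weeks 28 and 68. Observed r28 ran from 0.17 to 0.65 and the variance ratio from 0.97 to 0.59. The arm difference was essentially unbiased under both models.

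**Add or replace.** If r0 = 0.3 and r28 = 0.2, replacing week 0 by week 28 gives a ratio of (1 − 0.04)/(1 − 0.09) = 1.055, a variance about 5% larger. Adding week 28 to week 0 avoids this.

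**The case against.** The strongest reply is that nothing is wrong with the plan. Adjusting a change score for its own baseline is standard, the estimate is unbiased, and no margin, power statement or decision rule depends on these intervals. All of that stands. A reader might infer that the randomised comparison is biased or that the primary result is affected; the documents support neither.

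A second reply concerns size. A reader might take the r28 = 0.5 row as the expected loss, equivalent to about 30% more subjects (1/0.770 = 1.30). No document gives that correlation. Clear skin at weeks 20 and 28 may leave DLQI and PSSD near zero, and the gain is then 1–4% or nothing. The endpoint restricted to subjects with a week-28 PSSD sign score of at least 1 shows that some spread was expected. It does not show how much, and it also covers the non-super-responders in 2c. This reply stands too.

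Third, the Part 2 SAP is not among the documents, and the protocol leaves details to it. It may already have used a different covariate. The Synopsis wording makes week 0 likely but does not settle it.

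Fourth, a reader might carry the same gain over to 3a vs 3b. The documents do not support that:

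- Entry to Part 3 requires PASI below 3 at week 68, a selection made after randomisation. Per the Overall safety SAP, 273 of the 297 randomised subjects entered.
- Of those 273, 227 (83%) were re-treated by week 220.
- Part 3 SAP section 5 follows such subjects only to R0, and 5.1.8 uses LOCF for continuous endpoints. Many late values would then be relapse-visit scores, for which a correlation with week 28 cannot be presumed.

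**Conclusion.** The point holds as a minor efficiency suggestion for the week-68 comparison of 2a and 2b in DLQI and PSSD. Three facts are clear from the documents: randomisation at week 28, week 0 as the only score covariate in the protocol, and week-28 scores collected before the first randomised dose. The planned model remains valid.

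The size is uncertain. It rests on assumed correlations and runs from no gain to about 12% at r28 = 0.5. It becomes material only from about r28 = 0.4 upward. No gain is claimed for Part 3 or for BSA.

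**What to change.** Keep change from week 0 as the endpoint and keep the week-0 covariate. Add the week-28 score as a second covariate in the week-68 2a-vs-2b ANCOVAs of DLQI and PSSD (Protocol 11.3 and 11.8).

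SAP section 1 records that the Part 2 analysis has been performed, and Protocol section 5 has the sponsor unblinded after the week-68 lock. The model should therefore be reported as a labelled supplementary analysis beside the planned one, not in place of it. Reporting the observed week-28 to week-68 correlation with it would show whether the adjustment mattered.

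The same term may be added as an optional supplementary model for 3a vs 3b (Part 3 SAP 5.5.3.2 and 5.5.3.5), with no precision gain promised.

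The cost is one degree of freedom per model and a supplementary table that is post hoc for Part 2. No new data are needed.
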